EFFECTS OF SMOKING ENVIRONMENTS ON BRAIN REACTIVITY

Principal Investigator:

F. [name].

Co Investigator:

[name].

PURPOSE

The goal of this study is to evaluate correlations between brain reactivity (as assessed via fMRI following 24-h abstinence) and the amount of smoking in a specific location. We will use ecological momentary assessment (EMA) to ask smokers to rate their exposure to, and smoking in, specific personal smoking environment cues (PSEs) over the course of 2 weeks before quitting smoking and 2 weeks after quitting smoking. Establishing that such correlations exist will provide strong evidence on the functional neuroanatomy of drug-context memory formation and retrieval.

BACKGROUND

Encountering an environment in which smoking has regularly occurred and/or its effects experienced, triggers strong craving and promotes lapse or relapse in smokers who have quit. Clinicians and recovery programs have long recognized the powerful influence of drug-environment associations and counsel patients to avoid “people, places, and things” associated with prior use. Confirming these intuitions, real-world assessment (i.e. ecological momentary assessment) of smoking suggests that relapse most often occurs in environments previously associated with smoking and that abstaining in contexts associated with smoking decreases the probability of later lapse.

Despite recognition of the influence of environment as a determinant of drug use and relapse, and despite a large and growing preclinical literature, surprisingly little empirical work has specifically addressed questions around drug-environment associations in humans. Laboratory-based studies have demonstrated that environments previously unassociated with smoking, when paired with or made predictive of smoking, can elicit urges to smoke. More recently, preference for a room paired with a low dose of amphetamine has been demonstrated in amphetamine-naïve subjects and has been suggested as a human analog of conditioned place preference (CPP). Collectively, this and other cue-conditioning research in humans provides insight into the formation of drug-environment associations but leaves open questions regarding the influence of *real-world environments* on subjective experience, behavior and brain function among individuals with long drug use histories.

DESIGN AND PROCEDURES

We propose to obtain consent from a total of 200 participants in order to identify 48 who meet all inclusion and exclusion criteria and complete all aspects of the study. During a phone screening interview, the study will be described in detail and preliminary participant characteristics (e.g. age, number of cigarettes per day) will be assessed. Those participants who meet criteria for participation will be invited to our offices for an informed consent and screening visit.

Screening session. During screening, all aspects of the study will be described to subjects and informed consent will be acquired. Breath and saliva samples will be collected in order to verify smoking status and blood alcohol level (BAL); and measures including, but not limited to, smoking

history, nicotine dependence, and mood will be collected. Vitals such as heart rate, blood pressure and weight/height will also be measured. Urine samples will be obtained in order to screen for illicit drug use and pregnancy status. Use of illegal drugs will be exclusionary. Marijuana use will not be exclusionary, but participants must agree to not use marijuana 24 hours prior to sessions and may not mix their marijuana with tobacco (i.e. blunts). Females who test positive for pregnancy will be excluded from the study and be given options for smoking cessation programs. Participants will also be interviewed regarding their smoking behavior including an assessment of contexts (places) in which they smoke and abstain from smoking cigarettes.

Inclusion criteria:

- 1) generally healthy [(i.e. ambulatory, not currently sick)]
- 2) between the ages of 18 and 65
- 3) smoking of at least 5 cig/day of a brand delivering ≥ 0.5 mg nicotine (FTC method) for ≥ 1 year
- 4) an expired CO concentration of at least 10 ppm (to confirm inhalation) or urinary cotinine >1000 ng/mL (NicAlert = 6).
- 5) interest in quitting smoking within the timeframe of the experiment.
- 6) ability to identify 4 personal smoking and 4 personal non-smoking places.
- 7) right handed as measured by a three-item scale used in our laboratory
- 8) own a smartphone
- 9) Breath Alcohol Level =0.000

Exclusion criteria:

- 1) immediate or no desire to quit smoking;
- 2) inability to attend all required experimental sessions;
- 3) use of other tobacco products or e-cigarettes more than 9 days in the past 30 days;
- 4) current alcohol or drug abuse;
- 5) positive toxicology screen for any of the following drugs: cocaine, opiates, methadone, benzodiazepines, barbiturates, amphetamines, methamphetamines, and PCP
 - a. marijuana will be tested for but will not be exclusionary;
 - b. participants failing the toxicology screen will be allowed to re-screen once;
- 6) current use of psychoactive medications per self-report or urine screen
- 7) current use of nicotine replacement therapy or other smoking cessation treatment;
- 8) screening systolic BP greater than 140 (participants failing for blood pressure will be allowed to rescreen once)
- 9) screening diastolic BP greater than 90 (participants failing for blood pressure will be allowed to rescreen once)
- 10) presence of conditions contraindicated for nicotine replacement therapy (e.g., skin allergies)
- 11) report of significant health problems including but not restricted to (e.g. chronic hypertension, emphysema, seizure disorder, history of significant heart problems, heart disease, heart attack in the past 90 days, irregular heartbeat)
- 12) medical condition that may contraindicate participation in the opinion of the investigator and study physician.
- 13) current major psychiatric disease such as schizophrenia or schizoaffective disorder
- 14) currently pregnant, breast feeding or likely to become pregnant;
- 15) a quit attempt resulting in greater than 3 days of abstinence in the past 30 days
- 16) presence of conditions that would make MRI unsafe (e.g., pacemaker)

17) problems with vision that cannot be corrected with contacts or glasses

Among females, pregnancy at screening as measured by a urine test will be exclusionary. Females of child bearing potential must agree to use appropriate contraception during the course of the study.

They must further agree to notify the study staff if they become pregnant during the study. If the urine pregnancy test is negative and subject meets all other inclusion criteria, an additional urine pregnancy test will be conducted at the scanning session.

Participants will be asked to indicate in the consent form whether they would like to be contacted about future studies while the present study is ongoing. Participants will be informed there is no obligation to participate and their refusal for future contact will in no way affect their participation in this study.

Training session. Participants will be introduced to the digital camera they will use to capture images of their personal environments. All information regarding the recording of events, the taking of pictures and operation of the camera (e.g. recharging, storage) will be reviewed with the participant. Any questions from participants regarding the use of the camera will be discussed. Participants will also be allowed to take photos with their own personal devices and email them to the study staff. If participants choose to take photos with device(s) other than the camera provided, the device(s) must have a photo resolution of at least 72 dpi. In addition to assessing environments and training on camera use, all participants will be placed in the mock scanner. While in the mock scanner they will be familiarized with the fMRI cue-reactivity task and GGNG task. During the training session a breath CO sample will be collected.

Camera Turn-in session. Once participants have collected at least 32 photographs of personal neutral and smoking environments, participants will return to the lab with the camera. The images from the camera will be uploaded, examined, and reviewed with each participant to ensure enough useable pictures were taken. Participants will be instructed to review and remove any pictures of other people from the camera prior to uploading. After uploading the pictures, if the study staff discover any pictures of other people those images will be permanently deleted. Pictures taken by participants will become property of the Duke Center for Addiction Science and Technology (CfAST) for research purposes. A participant's pictures of any private location, such as a home, will not be shown to any other research participants in this or any other study. Any pictures of public places (bus stop, restaurant, etc.) may be used and shown to participants in future studies.

MetricWire Mobile Application: Following the picture review, participants will be trained on how to download and use MetricWire, a mobile application (app) on a smartphone and how to answer study related questions on the app. After the Camera Turn-in session participants will be randomly prompted to answer questions, including items related to craving and mood, on the mobile app up to 6 times throughout the day. Participants will also be asked fill out a survey on the app each time they smoke a cigarette. Participants will be compensated \$0.50 for each of the 6 prompted surveys completed (\$3.00 maximum daily amount)

GPS Logger- Participants will carry a GPS device with them for two weeks prior to the quit date and two weeks after the quit date. The GPS logger is a small device designed to measure and record location by triangulating signals transmitted from earth orbiting satellites. The unit we will use is about the size of a cigarette lighter and is rechargeable. When operational, the GPS unit will continuously record participant location and this information will be later downloaded onto a secured server with limited access. Participants will be required to keep the GPS on and with them at all times during the 4 week period except when it might become wet (bathing, showering, swimming) or when sleeping. Participants

will be provided with detailed instructions on how to operate and recharge the unit. Participants will receive \$2.50 per day for carrying the device and providing high quality GPS tracking (i.e. no evidence of leaving it in one location for the entire day). Participants will also receive a \$75 bonus for 4 weeks of compliance with GPS tracking and MetricWire surveys.

Nicotine Patches:

Participants will wear Nicotine patches (Nicoderm CQ®): 21mg/day patches for 6 weeks, then step down to 14mg/d patches for 2 weeks and finally step down 7mg/d for the last 2 weeks of study protocol. If the participant smokes less than 10 cigarettes/day, we will start them on 14mg/day patches for 6 weeks before stepping down to 7mg/day patches for the final 4 weeks of treatment. Insomnia and abnormal dreams are common and expected side effects associated with 24 hour nicotine patches. If a subject complains of disturbed sleep, he or she will be instructed to remove the patch at bedtime and apply a new one the next day at the usual time. Skin irritation may occur, although this will be minimized by changing the site of patch application daily. Using 1% hydrocortisone cream on the affected area will be recommended to help reduce skin irritation. If a subject develops itching or a rash at the patch site, he or she will be advised to use 1% hydrocortisone cream on the affected area. Symptoms associated with nicotine toxicity include lightheadedness, dizziness, nausea, fainting and vomiting. Symptoms considered moderate to severe in nature will be evaluated by the study medical staff by telephone or in person, depending upon the level of severity. Upon evaluation, the subject will then be given the choice of continuing in the study while discontinuing patch use.

fMRI session. Following the picture taking phase, 1 fMRI session will take place. The fMRI session will begin following 24 hour smoking abstinence. 24 hour smoking abstinence will be verified by breath CO <6ppm. Female participants must provide a urine sample for pregnancy testing the day of the MRI scan. The test results must be negative in order to continue with the study. Prior to entering the scanner, participants will complete questionnaires regarding their current mood and withdrawal symptoms. Respiration and heart rate will be monitored during the scan to collect physiological data. Standard localizer and anatomical scans will be conducted followed by fMRI scanning. During fMRI scanning, participants will view pictures of personal and standard smoking and non-smoking environments; and also pictures of smoking-related (cigarettes, lighters, ashtrays) and non-smoking related objects (keys, tape dispensers, pencils). Participants will also complete a Go/Go/No-Go task consisting of three types of trials: frequent-Go, infrequent-Go, and No-Go trials. In the frequent-Go and infrequent-Go trials, subjects are required to press a button as quickly as possible, whereas in the No-Go trials, subjects are to refrain from pressing the button. For each trial, a colored circle is presented. The color of the circle indicates the type of trial: gray indicates a frequent-Go trial, and yellow or blue indicates the infrequent-Go or No-Go trial. The relationship between color (yellow/blue) and trials type (infrequent-Go/No-Go) is counterbalanced across subjects. After being removed from the scanner, participants will complete post-session mood and withdrawal questionnaires.

Breath alcohol levels will be assessed prior to the fMRI session and participants must record a BAL of 0.000. Participants who test positive for alcohol will be excluded from participation that day and asked to reschedule. Participants testing positive for alcohol on more than one occasion will be excluded from the study.

Lab Visits: Four lab visits will be conducted during the 10 weeks following the quit day. The visits will take place 1 week, 2 weeks, 6 weeks and 10 weeks post quit day. Each visit will have a window period of +/- 3 days from targeted date, calculated from date of camera return visit. Visits exceeding the window period will be recorded as a protocol deviation. These visits will be largely identical except that instructions and reminders to participants about upcoming events will vary from session to session. At each lab visit the following will be collected: vitals (heart rate, blood pressure and weight), breath CO and measures of smoking withdrawal and mood. Nicotine patches and instructions for using them will

be provided at each session. Advice on quitting and minimal support will be provided as requested at these visits. During the third lab visit participants will review and annotate their GPS tracks with study staff by indicating the name (e.g. home, work, library) of stay-points (i.e. places they spent more than 1 hour). Each lab visit will require 20-30 minutes of participant time.

6 month Follow-Up phone call. Participants will be contacted by phone 6 months after completing the study to complete a brief interview about current smoking status and nicotine dependence.

DATA ANALYSIS

The primary aim of the study is to examine differences in brain responses to personal vs. standard smoking and non-smoking environments. Multiple methods will be used to test hypotheses about brain functioning during cue-reactivity (CR): a region of interest (ROI) based approach for testing specific *a priori* hypotheses and a voxel-wise whole-brain analysis for identifying unexpected findings. This two-pronged approach to fMRI data analysis will allow us to maximally evaluate variability in signal over space and time while minimizing the risk of both Type I and II error. For each hypothesis, the brain CR variable of interest will be the difference in mean % signal change. We will examine correlation between brain responses to smoking environments (minus non-smoking environments) and smoking cessation outcomes (i.e. days to lapse, days to relapse).

Our EMA+GPS analysis will primarily focus on locations where smokers smoke before and after quitting smoking. We will first examine whether post-quit craving and lapse behavior occur in locations associated with smoking prior to quitting smoking. Moreover, we will evaluate whether being in locations associated with prior smoking (but not smoking) during the post-cessation period are associated with better treatment outcomes. Finally, based on GPS location and self-reported EMA location, we will assign smoking intensity values to personal smoking environments presented in the scanner. We will evaluate whether EMA-assessed smoking intensity values are correlated with brain responses to these personal smoking environments.

RISK/BENEFIT ASSESSMENT

Nicotine Patch: Insomnia and abnormal dreams are common and expected side effects associated with 24 hour nicotine patches. If a subject complains of disturbed sleep, he or she will be instructed to remove the patch at bedtime and apply a new one the next day at the usual time. Skin irritation may occur, although this will be minimized by changing the site of patch application daily. Using 1% hydrocortisone cream on the affected area will be recommended to help reduce skin irritation. If a subject develops itching or a rash at the patch site, he or she will be advised to use 1% hydrocortisone cream on the affected area. Symptoms associated with nicotine toxicity include, lightheadedness, dizziness, nausea, fainting and vomiting. Symptoms considered moderate to severe in nature will be evaluated by the study medical staff by telephone or in person, depending upon the level of severity. Upon evaluation, the subject will then be given the choice of continuing in the study while discontinuing patch use.

Women of childbearing potential: Pregnant or nursing women will be excluded from the study. Female participants will undergo a urine pregnancy test at screening. Subjects must also agree to use appropriate contraception during the course of the trial. Medically acceptable contraceptives include: (1) surgical sterilization (such as a tubal ligation or hysterectomy), (2) approved hormonal contraceptives (such as birth control pills, patches, implants or injections), (3) barrier methods (such as a condom or diaphragm) used with a spermicide, or (4) an intrauterine device (IUD). Women who smoke and are over the age of 35 should not take oral contraceptives that contain estrogen without consulting their physician. Smoking while using oral contraceptives can increase the risk of having a cardiovascular

event such as a heart attack or stroke. Additionally, there is a potential risk of thrombosis associated with hormonal therapy (including contraceptives) and smoking. They will be encouraged in the consent form to notify study staff if they believe a change in their pregnancy status has occurred during the trial.

Management of side effects: Reports of side effects will be obtained by study staff and communicated to the principle investigator and study physician, who will determine the most appropriate course of action, which may include options for termination of study participation. Participants will be reminded of their option to withdraw from the study at any time. If a participant decides to withdraw from the study, we will ask them to return for a final visit to return all study materials. In the event of significant side effects it will be necessary to reduce patch dosage. In response to complaints of insomnia, instructions will be given to remove skin patches at bedtime. In the event of other intolerable side effects patches will be discontinued completely.

MRI: MRI provides clinically relevant anatomic and functional information non-invasively and with minimal risk, if the well-known contraindications (such as pacemakers) and potential hazards (such as attraction of metallic objects) are avoided.

Do you feel that there is any risk to wearing the GPS tracker and having their whereabouts known? I recognize that smart phones and activity trackers have this feature, but you are specifically providing them with a GPS tracker for tracking purposes for the study.

PARTICIPANT RECRUITMENT AND COMPENSATION

We will advertise in local newspapers, the radio, tv, flyers on bulletin boards, Facebook and on the internet (including but not limited to trianglesmokingstudies.com and craigslist). When we receive calls from potential subjects we will return their call and ask information including name, address, age, and smoking history. They will be given a brief description of our studies and will be asked questions to determine interest and eligibility. If they do qualify we will schedule a screening session where we will follow all IRB protocols of informed consent.

We will utilize medical records querying systems to identify and pre-screen possibly eligible subjects. After a report is generated from the medical records of patients meeting our defined criteria, they will be sent an invitation to participate in the study through their Duke patient portal. Patients can indicate on the portal whether or not to seek more information about the study which will send a communication to the research team. Those who indicate interest in participating will be contacted by the research team to proceed to the initial phone screening phase (as described above).

Participants will receive \$25 at the screening session if they pass the drug test, breath alcohol test and CO test. Individuals who do not pass these tests will be dismissed from the screening visit without payment, except in the event they can produce a current, valid prescription for the medication that caused them to fail the drug test. Participants will also receive \$25 for completing the training session, \$25 for the camera return visit plus \$25 if they returned complete and useable photos within one week of the training session, \$100 for the fMRI session, \$30 for each post-quit lab visit (\$120 total) and a \$100 at the end of the study if they complete all sessions (up to \$420 total). Participants may also earn \$5.50 each day they complete their MetricWire surveys and GPS logging, with a \$75 bonus for 4 weeks compliance with GPS tracking and MetricWire surveys.(up to \$229). Participants will also receive \$10 for completing a 6 month post quit date follow-up phone call. Participants that decide to withdraw from

the study before fulfilling all of the requested tasks will be given compensation for completed study tasks.

DATA AND SAFETY MONITORING

The Principal Investigator will report all serious adverse events and unanticipated findings and problems relating to the study in an expedited manner to the Duke University Health System (DUHS) Institutional Review Board (IRB) office and all applicable regulatory authorities in accordance with standard operating procedures.

COSTS TO PARTICIPANTS

There are no costs to participants for taking part in this study. All the study costs, including any procedures related directly to the study, will be paid for by the study.

DATA STORAGE AND CONFIDENTIALITY

Participants will be informed, in their consent forms, of the data storage and confidentiality safeguards, which are practiced according to current HIPAA regulations.

Except when required by law, the participant will not be identified by name, social security number, address, telephone number or any other direct personal identifiers in the study records.

All photographic images acquired by participants will be reviewable by participants prior to upload to the secure server. Data from the server can only be accessed by authorized study staff with a username and password. All photographs of private locations taken by participants will be destroyed by the PI or CRC upon completion of the study. Photographs that include persons not known to subject will be deleted. The participant will be assigned a unique code number and the key to the code will be kept in a locked room accessible to the study coordinator.

This study uses a mobile app named MetricWire to collect data. MetricWire is a company based in Canada. The data submitted in the app is stored in the United States, by a company called Amazon Web Services, which is based in Virginia. While MetricWire will not access data that is submitted using the app, they have logical access to the data. This means that it is possible that they could view the data. The study team has executed a research contract with MetricWire that has research controls embedded by the Information Security Office. Participants will be fully informed during the consent process on both the above information about MetricWire specifically and the limits of confidentiality related to the use of mobile apps more broadly.

At the initial session, study staff will log participants into the MetricWire app using a unique username and password. This username and password will be set by the study staff and will contain no identifying information. All smartphone electronic diaries and ecological momentary assessments will be treated as confidential.

Use of a personal phone: Participants who choose to use their personal smartphone for the study will receive instructions on how to install the app on their phone and study staff will assist with the installation. The study team will also provide instructions on how to remove the app from their device at the end of the study. Thus, while we acknowledge that a breach of confidentiality is possible, the likelihood is very low.

[name] at UPMC will be a collaborator for the study. She is listed as outside key personnel and will not have access to any study PHI or identifiable information.

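### The correlation of brain response with days to lapse or relapse has no analysis set or censoring rule, and the only stated sample is 48 completers

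*Combined protocol and SAP*

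**What the plan says.** Design and Procedures plans for 200 people to give consent. The stated aim of that number is to "identify 48 who meet all inclusion and exclusion criteria and complete all aspects of the study". No other sample is described, and no drop-out rate, effect size, alpha or power is given.

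What a completer must do is set out under Lab Visits: "Four lab visits will be conducted during the 10 weeks following the quit day", at 1, 2, 6 and 10 weeks.

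Data Analysis states: "We will examine correlation between brain responses to smoking environments (minus non-smoking environments) and smoking cessation outcomes", naming days to lapse and days to relapse. Neither term is defined. The predictor is given as follows: "the brain CR variable of interest will be the difference in mean % signal change". The section names no analysis set, no censoring rule and no rule for missing outcomes. On error control it says only that the two-pronged imaging approach works while "minimizing the risk of both Type I and II error".

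For people who withdraw, Management of side effects asks for a final visit to return materials and mentions no collection of smoking status. The six-month call is timed from completing the study in its own section, but from the quit date under Participant Recruitment and Compensation.

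**The concern.** Lapse and relapse accrue over the same weeks in which a participant becomes, or fails to become, a completer. Completer status is therefore a post-outcome variable. A plain correlation also needs a number of days for every person. A scanned participant who is lost before any known lapse has none, and one who never lapses has only a lower bound. With no other set defined, the analysis could easily settle on the 48 completers.

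Two things are then at stake for this analysis: scans already acquired are not used, and, if leaving depends on relapse, the estimated association is distorted. The primary aim in Data Analysis (personal versus standard environments) and the goal under Purpose (brain reactivity versus amount of smoking in a location) do not use cessation outcomes, so this mechanism reaches them less directly.

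**Working it through.** **1. The plan's own figure.** 48/200 = 24%. This pools screen failures with later drop-out and cannot be split. The 48 cannot be reproduced, because no design inputs are stated. For reference only, with two-sided 5% alpha, n = ((z₀.₉₇₅ + z_power)/atanh r)² + 3. For r = 0.40 and 80% power: (1.960 + 0.842)/0.4236 = 6.61; 6.61² + 3 = 46.7, so 47. By the same formula, n = 48 gives 80% power for |r| of about 0.39 and 90% for 0.45, provided all 48 have an outcome value.

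**2. Who has an outcome value.** There are four kinds of scanned participant.

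| Participant | Days to lapse | In completer set? |
|---|---|---|
| Lapses, attends to week 10 | Known if dated | Yes |
| Never lapses, attends to week 10 | Only a lower bound | Yes |
| Lapse recorded, then stops attending | Known | No |
| Lost before any known lapse | Only a lower bound | No |

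A completer analysis drops the last two rows. A plain correlation must also invent a value for the second. A censored time-to-event model uses all four.

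**3. Scans not used (rates assumed).** Suppose 70% relapse, and 90% of abstainers and 50% of relapsers complete. Completion is 0.3 × 0.9 + 0.7 × 0.5 = 0.62. Then 48/0.62 is about 77 scanned, so about 29 scans fall outside the completer set. If completion were 70% in everyone, 48/0.70 is about 69 scanned and about 21 are unused, with no bias.

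**4. Effect on the correlation (rates assumed).** A simulation of 2,000,000 draws took brain response and latent time to relapse as bivariate normal, true |r| = 0.40, with time capped at the end of follow-up. Completion was 90% in abstainers and 50% in relapsers. The all-scanned column assumes that outcomes are known for drop-outs. Power at n = 48, Φ(atanh(r)·√45 − 1.96), is in brackets. For example, |r| = 0.282 gives 0.290 × 6.708 − 1.960 = −0.015, or 49%.

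| Relapse | All scanned | Completers, drop-out unrelated to lapse timing | Completers, earliest relapsers lost most |
|---|---|---|---|
| 50% | 0.34 (67%) | 0.32 (62%) | 0.24 (38%) |
| 70% | 0.37 (75%) | 0.38 (76%) | 0.28 (49%) |
| 80% | 0.38 (78%) | 0.40 (81%) | 0.30 (55%) |

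The first column shows that giving never-lapsers the last day of follow-up already lowers 0.40 to 0.34–0.38. At 70% relapse, equal completion in relapsers and abstainers (90%/90% or 70%/70%) leaves 0.37 unchanged. Across the wider grid (true |r| 0.3–0.5, relapse 50–80%, relapser completion down to 30%), unequal completion changed |r| by −0.06 to +0.02 when drop-out was unrelated to timing. It lowered |r| by about 0.01 to 0.15 when the earliest relapsers left most.

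**5. Effect in a time-to-event model (rates assumed).** Cox simulations used a true hazard ratio of 1.5 per SD and about 33% lapse-free at 10 weeks. Drop-out was 40–75% of those lapsing within 2 weeks, 25–40% of later lapsers and 10% of non-lapsers, with 68–96 scanned and on average 52–60 completers.
- Hazard ratio: 1.52–1.56 in all scanned with censoring, against 1.56–1.64 in completers. Part of the excess over 1.5 is small-sample inflation.
- Power when EMA (the phone diary) recorded at least half of the early lapses: 67–80% against 64–73% in completers.
- Power when EMA recorded none of them: 61–65% against 68–71% in completers.

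Here the completer bias is away from the null. In step 4 it is mostly towards it.

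**The case against.** The strongest reply is that the 48 is a recruitment target. A reader might infer that the plan restricts the analysis to those 48, discards the scans of people who leave, or replaces early relapsers with people who stay. The documents do not support this: no section says so, and recruiting until 48 complete removes nobody. A reader might also infer that relapsers are the likeliest to leave. No passage says that either. Relapse does not end participation; the $30 per post-quit visit and the $100 for completing all sessions do not depend on abstinence; and "inability to attend all required experimental sessions" is an exclusion criterion. Nor does the plan estimate an abstinence rate that could be inflated.

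Some lapse data are also protected. Participants are asked for an app survey at each cigarette, and Purpose has EMA running for two weeks after quitting, so an early lapser who later leaves may already have a dated lapse. Finally, censoring at last contact may itself be informative, and step 5 shows that it can cost power.

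All of this stands, and it makes the point conditional. It does not supply an analysis set or a censoring rule, and it does not give a plain correlation a value for people who never lapse or are lost first. Relapse-related drop-out also remains plausible: the survey at each cigarette adds work for which no payment is stated, and the visits offer patches and quitting advice that may matter less to someone who is smoking again.

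**Conclusion.** The point holds as an omission combined with an unsuitable method. The only stated sample is defined by completion, completion is decided after the outcome can occur, and a plain correlation cannot use days to lapse or relapse properly. Bias follows only if the analysis falls back on completers and drop-out depends on relapse; the second condition is an assumption. Under assumed rates the effect on the correlation runs from none to a loss of about 0.15, with slight inflation in some patterns, and the hazard-ratio bias is modest and in the other direction. Size and sign therefore depend on a drop-out pattern that the documents do not describe. The loss of usable scans does not need relapse-related drop-out, only a completer analysis. The point concerns the brain–cessation analysis and should be fixed before that analysis is run; it does not undermine the primary contrast.

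**What to change.** For the brain–cessation analysis:
- Define the analysis set as every participant with a usable scan and a quit day, whatever their later attendance, and state the target of 48 in those terms.
- Replace the plain correlation with a time-to-event model (for example Cox, with brain response as a continuous covariate). Define lapse and relapse, take lapse dates from EMA and visits, and censor at the last contact at which smoking status was known.
- Add a sensitivity analysis that counts loss as lapse just after last contact, because censoring may be informative. Report completion by lapse status.
- Show completers only as a secondary analysis.
- Ask for smoking status from those who withdraw. The visit list names breath CO, withdrawal and mood but no dated smoking recall. Either add one or treat lapses first found at weeks 6 and 10 as interval-censored.

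The cost is wording in Design and Procedures and Data Analysis, plus at most a short question at contacts already planned. No extra participants are needed, and scans already acquired are used. The change should not be presented as a large gain in power: the gain is a few points if EMA caught at least half of the early lapses, and a loss if it caught none.
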